## 5.5 PREMATURE TERMINATION OR SUSPENSION OF STUDY

This study may be temporarily suspended or prematurely terminated if there is sufficient reasonable cause. Written notification, documenting the reason for study suspension or termination, will be provided by the study PI to IND sponsor. If the study is prematurely terminated or suspended, the PI will promptly inform the IRB and will provide the reason(s) for the termination or suspension

Circumstances that may warrant termination or suspension include, but are not limited to:

- Determination of unexpected, significant, or unacceptable risk to participants;
- Demonstration of efficacy that would warrant stopping;
- Insufficient compliance to protocol requirements;
- Data that are not sufficiently complete and/or evaluable;
- Determination of futility.

A suspended study may resume once concerns about safety, protocol compliance, data quality are addressed and satisfy the IRB and/or FDA

## 6 STUDY AGENT

### 6.1 STUDY AGENT(S) AND CONTROL DESCRIPTION

#### 6.1.1 ACQUISITION

Resveratrol liquid manufactured by Reserveage Nutrition will be purchased by the study. Placebo formulated by [name], Pharmacist at The Compounding Shop (<http://mycompoundingshop.com/>) will be purchased.

### 6.1.2 FORMULATION, APPEARANCE, PACKAGING, AND LABELING

Resveratrol liquid manufactured by Reserveage Nutrition will be tinted to match placebo color and repackaged in standard amber plastic bottle and relabeled so that the study participants will not know whether the compound is placebo or resveratrol. Placebo formulated to taste similar to the resveratrol liquid and be similar in appearance will be packaged in standard amber plastic bottle and labeled so that the study participants will not know whether the compound is placebo or resveratrol. Bottles will be labeled with participants name. This work will be performed by The Compounding Shop at [name]; [contact]; [contact].

### 6.1.3 PRODUCT STORAGE AND STABILITY

Resveratrol and placebo are stable at room temperature for extended periods of time but the manufacturer recommends storage in the refrigerator after opening. The participants will be instructed to store the opened supplement in the refrigerator.

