### 6.1.4 PREPARATION

As mentioned in section 6.1.2, resveratrol liquid will be tinted to match placebo color prior to repackaging. The packaged supplement and placebo are ready to be administered as is when supplied to the participants and do not require any further preparation or dilution.

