### 6.1.5 DOSING AND ADMINISTRATION

Based on the manufacturer's recommendation, the adult dosage is 125 mg/day or 5 ml of resveratrol reserveage liquid (<http://reserveage.com/product/resveratrol-cellular-age-defying- tonic/>). Four clinical trials have shown mild to moderate adverse gastrointestinal side effects associated with high levels of resveratrol 0.5- 5 g/day. and Resveratrol for Alzheimer's disease at [clinicaltrials.gov](http://clinicaltrials.gov). While at least many other studies did not show or discuss adverse events. Our study dosages at 125 mg/day for adults are far below these levels. Self administration for participants. Participants should take study medication 30 min prior to breakfast.

Serving Size: 1 tsp (5 mL)		
Servings per container: 30		
Amount per serving		% Daily Value*
Calories	10	-
Calories from Fat	0	-
Total Carbohydrate	2g	0%
Sugars	2g	-
Super Berry Blend Blueberry (fruit), Pomegranate (fruit), Goji (fruit), Organic Muscadine (grape and seed) Extract, Açai (fruit) and Mangosteen (fruit).	225 mg	-
Pro-Longevity Factors® Blend Wildcrafted Japanese Knotweed Extract (Polygonum cuspidatum) (root and rhizome) (standardized to contain 125 mg of transResveratrol), Organic French Whole Red Wine Grape (Vitis vinifera) (skin, seeds, fruit, stem, vine), certified Organic Muscadine Whole Red Grape (Vitis rotundifolia) (skin and seed)	130 mg	-
*Daily Value not established		
Other Ingredients: Purified water, organic agave, raspberry concentrate, natural flavors, potassium sorbate and xanthan gum.		

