#### 6.1.10 TRACKING OF DOSE

Doses are administered by the participants with 30 day supply mailed out monthly or 90 day supply for international participants.

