### 6.2 STUDY AGENT ACCOUNTABILITY PROCEDURES

Resveratrol and placebo will be received by the study team from The Compounding Shop at [name]; [contact]; [contact] and stored at room temperature in a secure location. Study coordinator will be responsible for mailing resveratrol and placebo to participants based on their randomized arm and a log will be kept recording drug/placebo identifier and to whom it is mailed. Study coordinator will be responsible for collecting the unused supplement and placebo from participants.

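### The pharmacy opens, tints and rebottles the resveratrol, yet the protocol keeps that stock at room temperature and applies the refrigerate-after-opening advice only once the participant opens a bottle

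*Combined protocol and SAP*

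**What the plan says.** Handling is spread over several parts of protocol section 6.

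- **Pharmacy step, resveratrol (6.1.2).** "Resveratrol liquid manufactured by Reserveage Nutrition will be tinted to match placebo color and repackaged in standard amber plastic bottle". Section 6.1.4 gives the order: "resveratrol liquid will be tinted to match placebo color prior to repackaging".
- **Pharmacy step, placebo (6.1.2).** "Placebo formulated to taste similar to the resveratrol liquid and be similar in appearance will be packaged in standard amber plastic bottle". The placebo is made and bottled at the pharmacy; it is not taken out of another maker's container.
- **Stability (6.1.3).** Both products are called stable at room temperature for long periods, without a duration, data or a reference. The same sentence then turns with a 'but' to the statement that "the manufacturer recommends storage in the refrigerator after opening". Participants are told to refrigerate a bottle once it is opened.
- **Study stock (6.2).** Product received from the pharmacy is "stored at room temperature in a secure location". No maximum time is given. The log described there records a drug or placebo identifier and the recipient.
- **Supply (6.1.10).** "30 day supply mailed out monthly or 90 day supply for international participants". Section 4.1 adds that non-international participants receive each supply 5 days before the end of a 30-day period.
- **Container (6.1.5).** The product label gives 5 mL per serving, 125 mg trans-resveratrol per serving, and "Servings per container: 30".

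**The concern.** The manufacturer's advice is tied to opening. The protocol starts that clock when the participant opens the study bottle. For resveratrol, the manufacturer's container was opened earlier, at the pharmacy, when a tint was added and the liquid was moved. On its face, the protocol therefore departs from the advice it cites between repackaging and the participant's first use of each bottle.

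What is at stake is whether the content of the active product is assured. A loss of content would touch the resveratrol period and leave the placebo period alone. If a smaller content gives an equal or smaller effect, the within-participant difference shrinks. A null result could then not be separated from a weak product. The protocol describes no record of repackaging date, so product age could not be reconstructed afterwards. Section 10.4.7.2 stresses that the patient pool is finite, which makes a repeat trial hard.

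**Working it through.** No sample-size or power figure in the plan depends on this point. The check is a comparison of sections plus simple supply arithmetic.

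**1. Is the resveratrol opened before the participant has it?** Sections 6.1.2 and 6.1.4 require a tint to be added and the liquid to be moved to another bottle. Neither uses the word opened, but neither step is possible with the container closed. Section 6.1.2 assigns this work to the pharmacy, and 6.2 has the study team receive the product from that pharmacy. So the room-temperature stock in 6.2 is the repackaged product.

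**2. Which condition applies to that stock?**

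| Stage | Manufacturer's container already opened? | Storage stated |
|---|---|---|
| Study stock (6.2) | Yes | Room temperature, no limit |
| Mailing | Yes | Not stated |
| At home, bottle not yet started | Yes | Not stated |
| At home, bottle in use (6.1.3) | Yes | Refrigerator |

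The cited advice is followed only in the last row.

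**3. Supply arithmetic from the label in 6.1.5.**
- Strength: 125 mg / 5 mL = 25 mg/mL.
- Container: 30 × 5 mL = 150 mL, which is 30 days at 5 mL per day.
- One 90-day period: 90 × 5 mL = 450 mL, and 450 / 150 = 3 containers' worth.

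**4. Waiting time at home before a bottle is started.** Section 7.3.3 tells participants to start the next 30-day aliquot and asks for a photo of the empty bottle at month's end. The schedule in 7.3.7 repeats the bottle request monthly. This points to 30-day bottles, although no section says outright that the international supply is divided that way. On that reading:
- Non-international, second and third bottles: about 5 days (4.1).
- International, bottle *k* of 3: 30 × (*k* − 1) days from the start of the period, that is 0, 30 and 60 days.

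Time in study stock and in transit comes on top for everyone and is not stated.

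**5. Can the delivered content be calculated?** No. The documents give no degradation rate and describe no assay. As pure assumption, a loss of 0%, 10%, 20% or 30% would leave 125 × (1 − loss) = 125, 112.5, 100 or 87.5 mg per day. Nothing in the documents favours any value above 0%.

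**The case against.** The strongest reply is that 6.1.3 does declare both products stable at room temperature. The placebo exists only as the pharmacy's preparation, so the sentence can be read as covering study product as supplied, and 6.2 fits that reading. The protocol also gives no reason for the refrigeration advice. The ingredient list in 6.1.5 is a water-, agave- and fruit-based liquid, so the advice need not concern trans-resveratrol content at all.

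Part of this stands: it rules out saying that the product is weaker than labelled. It does not settle the storage question. The stability sentence has no duration or source, is set against the after-opening advice in the same breath, and does not mention tinted or rebottled liquid.

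A reader might also infer four stronger things that the documents do not support.

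- *That all study bottles are affected.* Only the resveratrol is tinted and moved from another container.
- *That international participants in their third month fare worst.* Theirs is the longest home wait that can be worked out, but repackaging dates are not given. A bottle for a US participant may have stood as long in study stock.
- *That one bottle serves 90 days.* Sections 7.3.3 and 7.3.7 point the other way.
- *That a definite amount of power is lost.* This would need an assumed loss, an assumed proportional dose-response and an assumed true effect. The result would describe any trial built on those assumptions, not this one.

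**Conclusion.** The inconsistency holds. The protocol cites a storage condition that begins at opening, has the pharmacy open the resveratrol, and then stores it outside that condition for an unlimited time, without stability evidence for the liquid in its repackaged form.

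The measurable size is time. The home wait is about 5 days for a non-international participant's later bottles and about 60 days for an international participant's third, plus unstated stock and transit time. The 60-day figure assumes 30-day bottles and receipt at about the start of the period.

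The effect on the result is a possibility only. Its direction, toward no difference, assumes that less content never gives more effect. On that assumption the problem would make a null result harder to interpret but would not create a false positive. This is a worthwhile correction at low cost, not a demonstrated threat to the trial.

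**What to change.** Reconcile 6.1.2 to 6.1.4 with 6.2:

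- State that, for storage purposes, opening means repackaging at the pharmacy.
- Keep repackaged resveratrol under the manufacturer's after-opening condition until mail-out. Treat placebo identically, so that handling does not reveal the assignment.
- Tell participants to refrigerate every bottle on receipt, whether or not it has been started.
- Put the repackaging date (for placebo, the packaging date) and a lot code on the label and in the 6.2 log. Use the same code format for both products to protect the blind.

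Alternatively, keep room-temperature storage and cite stability evidence for the tinted, rebottled liquid over the longest storage time, including the 90-day international supply. A manufacturer's certificate for the lot would not be enough, because it describes the product before it was opened and tinted.

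The cost is refrigerator space, a label line, extra log columns and one instruction to participants. No added visit or procedure is needed. Mailing at ambient temperature remains; with the dates recorded, product age at use could at least be reported.

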### 6.1.4 PREPARATION

As mentioned in section 6.1.2, resveratrol liquid will be tinted to match placebo color prior to repackaging. The packaged supplement and placebo are ready to be administered as is when supplied to the participants and do not require any further preparation or dilution.

### 6.1.5 DOSING AND ADMINISTRATION

Based on the manufacturer's recommendation, the adult dosage is 125 mg/day or 5 ml of resveratrol reserveage liquid (<http://reserveage.com/product/resveratrol-cellular-age-defying- tonic/>). Four clinical trials have shown mild to moderate adverse gastrointestinal side effects associated with high levels of resveratrol 0.5- 5 g/day. and Resveratrol for Alzheimer's disease at [clinicaltrials.gov](http://clinicaltrials.gov). While at least many other studies did not show or discuss adverse events. Our study dosages at 125 mg/day for adults are far below these levels. Self administration for participants. Participants should take study medication 30 min prior to breakfast.

Serving Size: 1 tsp (5 mL)		
Servings per container: 30		
Amount per serving		% Daily Value*
Calories	10	-
Calories from Fat	0	-
Total Carbohydrate	2g	0%
Sugars	2g	-
Super Berry Blend Blueberry (fruit), Pomegranate (fruit), Goji (fruit), Organic Muscadine (grape and seed) Extract, Açai (fruit) and Mangosteen (fruit).	225 mg	-
Pro-Longevity Factors® Blend Wildcrafted Japanese Knotweed Extract (Polygonum cuspidatum) (root and rhizome) (standardized to contain 125 mg of transResveratrol), Organic French Whole Red Wine Grape (Vitis vinifera) (skin, seeds, fruit, stem, vine), certified Organic Muscadine Whole Red Grape (Vitis rotundifolia) (skin and seed)	130 mg	-
*Daily Value not established		
Other Ingredients: Purified water, organic agave, raspberry concentrate, natural flavors, potassium sorbate and xanthan gum.		

### 6.1.6 ROUTE OF ADMINISTRATION

Oral liquid

### 6.1.7 STARTING DOSE AND DOSE ESCALATION SCHEDULE

N/A

### 6.1.8 DOSE ADJUSTMENTS/MODIFICATIONS/DELAYS

N/A

### 6.1.9 DURATION OF THERAPY

90 days each of either placebo or resveratrol, with a month (30 days) of no medication in between the crossover administration.

#### 6.1.10 TRACKING OF DOSE

Doses are administered by the participants with 30 day supply mailed out monthly or 90 day supply for international participants.

#### 6.1.11 DEVICE SPECIFIC CONSIDERATIONS

N/A

### 6.2 STUDY AGENT ACCOUNTABILITY PROCEDURES

Resveratrol and placebo will be received by the study team from The Compounding Shop at [name]; [contact]; [contact] and stored at room temperature in a secure location. Study coordinator will be responsible for mailing resveratrol and placebo to participants based on their randomized arm and a log will be kept recording drug/placebo identifier and to whom it is mailed. Study coordinator will be responsible for collecting the unused supplement and placebo from participants.

## 7 STUDY PROCEDURES AND SCHEDULE

### 7.1 STUDY PROCEDURES/EVALUATIONS

#### 7.1.1 STUDY SPECIFIC PROCEDURES

- All potential participants will submit photos to confirm their PSACH diagnosis either by directly depositing photos into a secured encrypted server or via US mail (to be scanned and put into our secure data base and subsequently shredded).
- Medical history will be obtained by interview to confirm diagnosis of PSACH and to exclude those taking exclusion medications resveratrol, blood thinners, lovastatin, ketoconazole, itraconazole, fexofenadine, triazolam, Alfentanil, Cyclosporine, Dihydroergotamine, Dofetilide, Ergotamine, Fentanyl, Flibanserin, Oxycodone, Pimavanserin, Pimozide, Quinidine, Saquinavir, Sirolimus, Tacrolimus, Temsirolimus, Theophylline, Tizanidine, Thioridazine, Fosphenytoin, Phenytoin, or Warfarin. This information will be ascertained by the study staff over the phone and the participants will be asked to read the names of the medications and the dosages off the medicine containers. Information on medications will be collected for All medications the participant is on (both prescription and OTC). Exclusions will be made if any of the medications mentioned above are being used.
- Pain will be assessed to ensure that participants have pain to enroll in the study.
- For this 2X2 crossover design with two periods, patients will be randomized to one of two sequences, resveratrol/placebo or placebo/resveratrol. Those randomized to resveratrol/placebo will be given resveratrol in the first period and placebo in the second and vice versa for those randomized to the placebo/resveratrol sequence. Randomization will be carried out by our biostatistician so that investigators evaluating outcomes, along with participants, are blinded.
- Once enrolled into the study and randomized, a parcel will be mailed to the participants including all study materials including first month's study drug supply, study forms and pain logs.
- Monthly phone calls will be used to assess of adherence to protocol and will be logged into the study logbook by study staff. These phone calls will also include ascertainment of any changes to medications and diagnosis of any new health condition or pregnancy.
- Patient-reported daily pain logs will be mailed or emailed to study co-ordinator on a monthly basis.
- Platelet count below 50,000 per  $\mu\text{l}$  will result in exclusion from the study as this increases risk of bleeding with injury. A normal platelet count is around 140,000 to 450,000 platelets per microliter ( $\mu\text{l}$ ) of blood. When the number of platelets is low, this concentration reduces. Women normally experience a platelet count that varies slightly during the menstrual cycle and can fall near the end of pregnancy. The risk of bleeding increases as the platelet count drops, but bleeding problems are unlikely unless the count is less than 80,000-100,000 platelets per  $\mu\text{l}$ .

The following platelet counts carry the risk of serious bleeding:

Between 20,000 and 50,000 per  $\mu\text{l}$ : There is more risk of bleeding when injured.

Less than 20,000 per  $\mu\text{l}$ : Bleeding happens even without injury.

Below 10,000 platelets per  $\mu\text{l}$ : Spontaneous bleeding can be severe and a risk to life.

---

7.1.2 STANDARD OF CARE STUDY PROCEDURES

N/A

7.2 LABORATORY PROCEDURES/EVALUATIONS

---

7.2.1 CLINICAL LABORATORY EVALUATIONS

NA

---

7.2.2 OTHER ASSAYS OR PROCEDURES

NA

---

7.2.3 SPECIMEN PREPARATION, HANDLING, AND STORAGE

NA

---

7.2.4 SPECIMEN SHIPMENT

NA

7.3 STUDY SCHEDULE

---

7.3.1 SCREENING/ENROLLMENT (VISIT 0)

- Review medical photos to confirm diagnosis of PSACH.
- Review medical history to determine eligibility based on inclusion/exclusion criteria.
- Review medications history to determine eligibility based on inclusion/exclusion criteria.
- Review urine pregnancy test to determine eligibility based on inclusion/exclusion criteria.
- Obtain written informed consent from participants which can be scanned/photographed and emailed to [contact].
- Inform participants of eligibility and enrollment into the study.
- Provide participants with specific instructions needed to participate in the study.
- Schedule phone visits for eligible participants for the duration of the study.

---

7.3.2 ENROLLMENT/BASELINE

**Baseline Phone call (Visit 1, Day 0)**

- Patient will be contacted after receipt of initial study package via postal mail (including medications and information for blood draw to assess kidney function, liver function and blood cell count). The complete metabolic panel includes analysis of renal function [blood urea nitrogen (BUN), creatinine], liver function [total bilirubin, alanine aminotransferase (ALT), alkaline phosphatase (ALP), and aspartate aminotransferase (AST)], glucose, electrolytes [calcium, sodium, potassium, carbon dioxide (bicarbonate), chloride], protein [albumin, total protein]. The complete blood count (CBC) includes analysis of red blood count, hemoglobin, hematocrit, white blood cell count, platelet count. Platelet count below 50,000 per  $\mu\text{l}$  in CBC which indicates increased bleeding risk will result in exclusion.
- For Participants in the United States they will be asked to complete blood draw to the closest LabCorp or from their local facility at our cost. For the International participants blood need to be draw from a local facility an mailed to us for analysis at the local labcorp lab.

- Query participants about any changes in inclusion/exclusion criteria.
- Patients will be asked to start taking study medication on the next day.
- Administer HRQoL instrument.

